### 1.2 OBJECTIVE AND ENDPOINTS

**Table 1 - Objectives and endpoints**

	Objectives	Endpoints
Primary	

To evaluate the effect of BIVV020 on the durability of platelet response in participants with persistent/chronic immune thrombocytopenia (ITP)

	

Naïve participants: Proportion of participants with a platelet count <math>\geq 50 \times 10^9 / L</math> at <math>\geq 50\%</math> of scheduled visits, or for participants with baseline platelet count <math>< 15 \times 10^9 / L</math>, a <math>\geq 20 \times 10^9 / L</math> increase in platelet count from baseline at <math>\geq 50\%</math> of scheduled visits, without receiving rescue ITP therapy, as assessed from Week 3 to Week 24

Participants who previously received sutmilimab: Proportion of participants with maintenance of platelet count <math>\geq 30 \times 10^9 / L</math> at <math>\geq 50\%</math> of scheduled visits, without receiving rescue ITP therapy, as assessed from Week 3 to Week 24.

Objectives	Endpoints
Secondary 

• To assess the safety and tolerability of BIVV020

• To assess the pharmacokinetics (PK) of BIVV020

• To assess the response rate of treatment with BIVV020

• To assess the time to response

• To assess the effect of treatment with BIVV020 on the requirement for rescue ITP therapy

• To assess the immunogenicity of BIVV020

	

• Standard clinical and laboratory parameters and adverse events

• Plasma concentrations of BIVV020

• Response rate at Weeks 24 and 52, defined as a platelet count <math>\geq 50 \times 10^9 /L</math> and a greater than 2-fold increase from baseline, measured on 2 occasions at least 7 days apart, with the absence of bleeding (bleeding is defined as bleeding with a score <math>\geq 2</math> on the WHO bleeding scale), and the lack of combination ITP therapy during this period.

• Time from baseline to first platelet response, defined as greater than or equal to each of the following values: <math>50 \times 10^9 /L</math> and <math>100 \times 10^9 /L</math> (confirmed by 2 measurements at least 7 days apart)

• Proportion of participants who did not require rescue therapy for an acute episode of thrombocytopenia after Week 3

• Incidence and titer (if relevant) of anti-BIVV020 antibodies

Tertiary/exploratory 	

Objectives	Endpoints

## **2 SAMPLE SIZE DETERMINATION**

Approximately 12 participants will be enrolled. Since there is no statistical hypothesis to be tested in this study, the sample size is not determined statistically.

### 3 ANALYSIS POPULATIONS

The following populations for analyses are defined:

**Table 2 - Populations for analyses**

Population	Description
Enrolled	All participants from screened population who have been allocated to an intervention regardless of whether the intervention was received or not.
Intent-to-treat (ITT)	All exposed participants.
Safety	All enrolled participants who take at least 1 dose (including partial dose) of study intervention.
Pharmacokinetic (PK)	All enrolled and treated participants (safety population) with at least one post-baseline PK sample.
Pharmacodynamic (PD)	All enrolled and treated participants (safety population) with at least one post-baseline PD sample.
ADA	All enrolled and treated participants (safety population) with at least one post-baseline ADA sample.

## 4 STATISTICAL ANALYSES

Statistical analysis will be performed by Sanofi, using SAS® version 9.3 or higher and, where appropriate, additional validated software. This SAP is based on protocol Version 3, dated 25 January 2021.

### 4.1 GENERAL CONSIDERATIONS

In general, continuous data will be summarized using the number of observations available, mean, standard deviation (SD), median, (Q1, Q3 if applicable), minimum, and maximum. Categorical and ordinal data will be summarized using the count and percentage of participants.

The baseline value is defined as the last available value before the first IMP administration. For participants enrolled but not treated, the baseline value is defined as the last available value before enrollment. The baseline value for platelet count is defined as the average of the values before the first IMP administration (ie, platelet count collected during the D-56 to D-1 screening period and at 0 hour on D1).

#### *Observation period*

The observation period will be divided into 3 segments:

- The **pre-treatment period (or the screening period)** is defined as the period from the time of the signing of the informed consent form (ICF) to the first IMP administration.
- The **on-treatment period** is defined as the period from the first IMP administration to the last IMP administration +7 days.
- The **post-treatment period** is defined as the period after the on-treatment period.

The **treatment-emergent** (TE) period includes both on-treatment period and post-treatment period.

Analyses of safety will be based on the treatment-emergent period.

### 4.2 PARTICIPANT DISPOSITIONS

The number (%) of participants included in each of the analysis populations listed in [Table 2](#) will be summarized.

Screen failures are defined as participants who consent to participate in the study but are not subsequently enrolled. The number (%) of screen failures and reasons for screen failures will be provided in the screened population.

The number (%) of participants in the following categories will be provided:

- Enrolled participants
- Enrolled but not exposed participants

- Enrolled and exposed participants
- Participants who completed 24-week, 52-week, and the entire treatment period. A participant is considered as completed 24-week (52-week) treatment period if the participant was treated beyond study day 166 (study day 362 for Week 52).
- Participants who did not complete the 24-week, 52-week, and the entire treatment period and main reason for treatment discontinuation
- Participants who completed the study
- Participants who did not complete the study and main reason for study discontinuation.

In addition, the number (%) of participants screened, enrolled, discontinued treatment, discontinued study early will be provided by country and site.

#### Protocol deviations

Critical and major protocol deviations (automatic or manual) will be summarized in the enrolled population. Participants impacted by coronavirus disease 2019 (Covid-19) will be summarized upon data availability, such as discontinuation due to Covid-19, protocol deviation due to Covid-19, and visit(s) impacted by Covid-19 as collected in eCRF, etc.

### **4.3 PRIMARY ENDPOINT(S) ANALYSIS**

The primary endpoint is the proportions of participants who met the following criteria:

1. For naïve participants,
  - a platelet count  $\geq 50 \times 10^9/L$  OR
  - a  $\geq 20 \times 10^9/L$  increase from baseline if baseline platelet count  $< 15 \times 10^9/L$  at  $\geq 50\%$  of scheduled visits from Week 3 to Week 24.

For switchers, a platelet count  $\geq 30 \times 10^9/L$  at  $\geq 50\%$  of scheduled visits from Week 3 to Week 24.

2. No concomitant ITP therapy from Week 3 to Week 24.

Concomitant medications are defined in [Section 5.3](#). The ITP therapies will be identified by the Sanofi coding group, reviewed by medical, and defined in the programming specifications. The ITP therapies include corticosteroids, thrombopoietin receptor agonists, intravenous immunoglobulin, anti-D immunoglobulin, rituximab, fostamatinib, immunosuppressants (azathioprine, cyclosporin A, mycophenolate mofetil), cyclophosphamide, dapsone, danazol.

The response rate will be summarized for naïve participants, switchers, and total for the ITT along with the 95% exact Clopper-Pearson Confidence Interval (CI).

Platelet counts will be summarized by visit. These plots will also be provided:

- Individual platelet count profile: line plot of platelet count by visit for each participant

- Spaghetti plot platelet count by participant
- Median platelet count/change from baseline with by visit

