Participant diary ^t												X	X	X	
Phone calls ^u												X	X	X	X
Pharmacodynamics ^v															
Platelets ^w				X	X	X	X		X		X	X	X	X	X

	Screening/Transition period ^a	Loading dose		Weekly maintenance dosing								End of study			
				Weekly clinic visits					Visits every 2 weeks	Visits every 4 weeks	Visits every 8 weeks (minimum)				
Week		0				1-6					7-12 ^c	13-24 ^d	25+ ^e		
Day	D-56 to D-1	D1	D1	D1	D4 ^b	D8	D15	D22	D29	D36	D43	D44 - D85	D86 - D169	D170+	
Hour		0H	1H	4H											
Window					±1 d	±1 d	±1 d	±1 d	±1 d	±1 d	±1 d	±2 d	±3 d	±4 d	±14 d
BIVV020 dosing schedule															
Archival PD sample		PX00	PX01			PX02			PX03			PX04 ^y	PX05 ^r	PX06+	X
DNA sample for future research ^x		X													
Pharmacokinetics/ADA ^v															
BIVV020 plasma samples		P00	P01			P02	P03		P04		P05	P06 ^y	P07 ^r	P08+	X
Anti-BIVV020 antibodies		PD00							PD01			PD02 ^y	PD03 ^r	PD04+	X ^z

- ^a The Transition Period applies only to participants who were previously receiving sutimlimab, and is a period of at least 14 days between the last sutimlimab dose and the first dose of BIVV020. This period is included as part of the Screening Period.
- ^b The Day 4 visit may be performed at the participant's home using a home nursing service.
- ^c Visits will occur at Weeks 8, 10, and 12.
- ^d Visits will occur at Weeks 16, 20, and 24.
- ^e Visits will occur at Weeks 32, 40, 48, etc, with phone calls occurring approximately 4 weeks after each visit. Participants will continue to receive BIVV020 until the last participant enrolled has completed 52 weeks of treatment. For the last participant enrolled, a visit should occur at Week 52. Visits should occur around the time a participant is transitioning off BIVV020, even if this visit is less than 8 weeks from the prior visit. The maximum duration of treatment for an individual participant is 104 weeks.
- ^f Inclusion and exclusion criteria should be reviewed on Day 1 prior to enrollment.
- ^g Participants should have documented vaccination against encapsulated bacterial pathogens (*Neisseria meningitidis*, including serogroup B meningococcus [where available]), *Haemophilus influenzae*, and *Streptococcus pneumoniae*) within 5 years prior to enrollment. The participant should receive the vaccine series as early as possible. See [Section 8.2.6](#) for additional details.

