- ^h Testing includes HBsAg, HBcAb (IgG and IgM), anti-HCV Ab, and HIV test. Need for SARS-CoV-2 testing to be determined for each site. If SARS-CoV-2 testing is performed, a molecular test should be used.
- ⁱ FSH testing should be performed in participants with at least 12 months of amenorrhea. See [Section 10.4.1](#).

- j* Height at screening only.
- k* To be performed at Weeks 8 and 12 only.
- l* In addition to the IMP being dispensed in the clinic, the IMP may be dispensed for home administration via DTP services, except if prohibited by local regulatory authorities.
- m* Injections will be administered by site staff at visits that occur during Weeks 1 to 5. Participants will perform the injection in the clinic on Week 6 under the supervision of study staff.
- n* At visits that occurs from Week 7 onward, injections will be performed in the clinic by the participants, under the supervision of study staff.
- o* See [Section 8.2.2](#).
- p* See [Section 8.2.1](#). Ad-hoc physical exams may be performed at the discretion of the Investigator based on any AEs reported by the participant.
- q* See [Section 10.2](#) for a list of tests to be performed. Labs should be performed prior to drug administration.
- r* To be performed at Week 24 only.
- s* See [Section 8.2.7](#).
- t* Participants will record IMP administrations in a paper or e-diary when performing administrations at home.
- u* Phone calls will be performed to remind participants to take their injections, answer any questions they may have regarding the injections, and to assess AEs. From Weeks 7 to 24, phone calls will be performed on weeks that the participants are not seen in the clinic (Weeks 7, 9, 11, 13 to 15, 17 to 19, and 21 to 23). After Week 25, phone calls will be performed approximately 4 weeks after each previous visit. (If a visit during this period occurs within approximately 4 weeks of the prior visit, a phone call is not necessary.) Phone calls should continue to occur approximately every 8 weeks after the cessation of treatment, until the EOS visit.
- v* To be performed prior to drug administration unless otherwise noted.
- w* Platelet count should not be performed as a separate test at visits when a complete blood count is performed.
- x* If participant provided consent for future research.
- y* To be performed at Week 12 only.

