3 OBJECTIVES AND ENDPOINTS

Table 2 - Objectives and endpoints

Objectives	Endpoints
Primary 
To evaluate the effect of BIVV020 on the durability of platelet response in participants with persistent/chronic immune thrombocytopenia (ITP)	
Naïve participants: Proportion of participants with a platelet count $\geq 50 \times 10^9/L$ at $\geq 50\%$ of scheduled visits, or for participants with baseline platelet count $< 15 \times 10^9/L$, a $\geq 20 \times 10^9/L$ increase in platelet count from baseline at $\geq 50\%$ of scheduled visits, without receiving rescue ITP therapy, as assessed from Week 3 to Week 24.Participants who previously received sutmilimab: Proportion of participants with maintenance of platelet count $\geq 30 \times 10^9/L$ at $\geq 50\%$ of scheduled visits, without receiving rescue ITP therapy, as assessed from Week 3 to Week 24.
Secondary 
To assess the safety and tolerability of BIVV020To assess the pharmacokinetics (PK) of BIVV020To assess the response rate of treatment with BIVV020To assess the time to responseTo assess the effect of treatment with BIVV020 on the requirement for rescue ITP therapyTo assess the immunogenicity of BIVV020	
Standard clinical and laboratory parameters and adverse eventsPlasma concentrations of BIVV020Response rate at Weeks 24 and 52, defined as a platelet count $\geq 50 \times 10^9/L$ and a greater than 2-fold increase from baseline, measured on 2 occasions at least 7 days apart, with the absence of bleeding (bleeding is defined as bleeding with a score ≥ 2 on the WHO bleeding scale), and the lack of combination ITP therapy during this period.Time from baseline to first platelet response, defined as greater than or equal to each of the following values: $50 \times 10^9/L$ and $100 \times 10^9/L$ (confirmed by 2 measurements at least 7 days apart)Proportion of participants who did not require rescue therapy for an acute episode of thrombocytopenia after Week 3Incidence and titer (if relevant) of anti-BIVV020 antibodies

Objectives	Endpoints
Exploratory	

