## 1 INTRODUCTION

### 1.1 STUDY DESIGN

This is a Phase 2a, open-label, non-randomized, multicenter study to evaluate the efficacy, safety and tolerability of BIVV020 in adults with persistent/chronic primary ITP.

During the 56-day screening period, prospective participants will have a detailed medical history documented, physical evaluations and blood samples (including platelet count) collected. For participants receiving sutmilimab (BIVV009) in study TDR16218, they may continue to receive sutmilimab during screening, until at least 14 days prior to the first administration of investigational medicinal product (IMP) - BIVV020.

The study will enroll approximately 12 participants: up to 6 participants who have received and responded to sutmilimab (BIVV009) in study TDR16218 (switchers), as well as patients who have not previously received sutmilimab (naïve participants).

A loading dose of BIVV020 at 50 mg/kg intravenous (IV) will be administered on Day 1, followed by maintenance doses of 600 mg subcutaneous weekly starting on Day 8 until the last participant enrolled has completed 52 weeks of treatment. The maximum duration of treatment for a participant is 104 weeks.

The on-site visits will be conducted weekly from Week 1 to Week 6, biweekly from Week 7 to Week 12, every 4 weeks from Week 13 to Week 24, every 8 weeks after Week 24 until the end-of-study (EOS) visit. Platelet counts will be collected during the on-site visits.

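### The primary durability endpoint gives equal weight to visits on a front-loaded schedule, so an untreated participant below threshold at Weeks 12 to 24 can still count as a responder

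*SAP*

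**What the plan says.** The objective in SAP Table 1, as in Protocol Section 3, is "To evaluate the effect of BIVV020 on the durability of platelet response". SAP 4.3 turns this into two conditions that must both hold.

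- **Platelet condition.** The count is at or above threshold at 50% or more "of scheduled visits from Week 3 to Week 24". For naive participants the threshold is 50 x10^9/L, or a rise of at least 20 x10^9/L if baseline is below 15 x10^9/L. For switchers it is 30 x10^9/L.
- **Therapy condition.** There is no concomitant ITP therapy from Week 3 to Week 24. The protocol words this as no rescue ITP therapy.

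Neither document weights visits by the time they represent, asks for consecutive visits, or asks for response in the later part of the window.

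SAP 1.1 describes on-site visits as "weekly from Week 1 to Week 6, biweekly from Week 7 to Week 12, every 4 weeks from Week 13 to Week 24". The Schedule of Activities footnotes fix the later ones: "Visits will occur at Weeks 8, 10, and 12", then "Visits will occur at Weeks 16, 20, and 24". Two statements bear on which visits have a platelet count. SAP 1.1 says "Platelet counts will be collected during the on-site visits". In the Schedule of Activities, the platelet and haematology rows are both blank at D22 (Week 3) and D36 (Week 5).

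**The concern.** A proportion of visits stands in for a proportion of time only if visits are roughly evenly spaced. Here they are dense early and sparse late, so the 50% mark can be reached before the second half of the window begins. A response that fades by Week 12 can then be reported under a durability objective, even for a participant who attended every visit and has no missing data.

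This matters because the study is single-arm and tests no hypothesis. The responder proportion with its Clopper-Pearson interval is the main efficacy result, and what it means carries the conclusion.

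**Working it through.** The plan states no figure to reproduce, so the check counts visits and compares their share with the share of time.

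**Inputs.** Week w falls on day 7w + 1, so Week 3 is D22 and Week 24 is D169. The window is 169 - 22 = 147 days. The platelet row of the Schedule of Activities gives eight counts, on D29, D43, D57 (Week 8), D71 (Week 10), D85 (Week 12), D113 (Week 16), D141 (Week 20) and D169 (Week 24). Reading SAP 1.1 as a count at every on-site visit adds D22 and D36, making ten.

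**Front-loading.** D22 to D85 is 63/147 = 43% of the window and holds 5 of 8 counts (7 of 10 on the longer list). D85 to D169 is 84/147 = 57% and holds the other 3.

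**Earliest loss that still qualifies.** Visits needed are half the denominator, rounded up. Share of time is (last responding day - 22)/147. The midpoint version runs to halfway between the last responding visit and the next count. Both treat the participant as in response from D22.

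| Counts used | Visits in response | Score | To last responding day | Midpoint-weighted |
|---|---|---|---|---|
| 8 (Schedule of Activities) | D29, D43, W8, W10 | 4/8 | (71 - 22)/147 = 33% | (78 - 22)/147 = 38% |
| 8, Week 10 count lost | D29, D43, W8, W12 | 4/8 planned or 4/7 available | (85 - 22)/147 = 43% | (99 - 22)/147 = 52% |
| 10 (SAP 1.1 wording) | D22, D29, D36, D43, W8 | 5/10 | (57 - 22)/147 = 24% | (64 - 22)/147 = 29% |

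The second row arises because SAP Table 6 targets Week 10 at day 80 with a window of 2 days either side (days 78 to 82), while 7 x 10 + 1 = 71. If those windows also govern the responder count, an on-time Week 10 result falls outside. The participant must then respond through Week 12, but can still be below threshold at Weeks 16, 20 and 24.

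**The reverse case.** Response only at Weeks 12, 16, 20 and 24 scores 4/10 on ten visits, a non-responder with (169 - 78)/147 = 62% of the window in response. On the eight visits in the Schedule of Activities the same pattern scores 4/8 and is a responder.

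**Effect on the rate.** Reclassifying one of 12 participants moves, for example, 6/12 = 50.0% (95% CI 21.1 to 78.9) to 5/12 = 41.7% (15.2 to 72.3), a shift of 8.3 points. If six are naive (an assumption: about 12 in total less the maximum of six switchers), one participant is 1/6, or 16.7 points, in that group.

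**What the supportive rules would do.** A midpoint time-weighted rule at 50% rejects the first and third rows (38%, 29%) and passes the second (52%). A rule on Weeks 16, 20 and 24 rejects all three, since each has 0 of 3.

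**The case against.** The strongest objection is the therapy condition. A participant who loses response and is then given rescue, restarts a thrombopoietin receptor agonist or has a concomitant ITP drug increased is a non-responder whatever the visit count. The problem case therefore needs about 14 weeks below threshold without ITP therapy, and the documents give no frequency for that. This narrows the point considerably without removing it. A naive participant with baseline of at least 15 x10^9/L who drifts to 30-49 x10^9/L is below the endpoint threshold. Yet inclusion criterion I 03(b) treats a sustained count of 30 x10^9/L or more without bleeding as adequate, so going untreated is plausible. It is less so for switchers, whose threshold is already 30.

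The case also meets 50% exactly. One miss at any counted early visit makes the participant a non-responder. If the denominator were ten scheduled visits with only eight counts taken, five passes would be needed, which means response through Week 12.

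Late loss would also be visible. SAP 4.3 plans individual and spaghetti plots and by-visit summaries, which is useful with about 12 participants, but they yield no rate. SAP 4.4 adds a Week 24 response rate, but its two counts at least 7 days apart are not tied to visits near Week 24, and it needs a more than 2-fold rise from baseline, so it does not measure maintenance in switchers. The rescue-free proportions do not use platelet counts. The exploratory endpoints are blacked out, so a further durability measure there cannot be excluded.

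Finally, the 50% rule is pre-specified and the same in both documents. That stands: this concerns interpretation and is not a contradiction between protocol and SAP.

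**Conclusion.** The point holds in limited form. On the eight platelet visits in the Schedule of Activities, response that ends after Week 10 can be scored as meeting a durability endpoint, with 33% of the window in response (38% midpoint-weighted). This assumes all four early counts are above threshold and no ITP therapy is given from Week 3 to Week 24. If the Day 80 target for Week 10 is applied literally, the case becomes loss after Week 12, at about 52% midpoint-weighted.

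A reader might infer more than the documents support:

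- **That anyone who loses response after Week 8 or Week 10 is automatically a responder.** The therapy condition and the absence of any spare visit rule this out.
- **That loss after Week 8 qualifies, or that a late sustained responder fails.** Both need counts at D22 and D36, which SAP 1.1 implies but the Schedule of Activities does not show.
- **That early response merely reflects the IV loading dose.** Weekly SC maintenance starts on Day 8 and the dose rationale is largely redacted, so nothing here establishes that.

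**What to change.** Keep the protocol endpoint as primary. In SAP 4.3, pre-specify two supportive analyses from the same platelet counts and with the same therapy criterion:

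1. **Time-weighted.** Weight each visit's status by the interval it represents, midpoint to midpoint. Response means at least 50% of Week 3 to Week 24 time above threshold.
2. **Late-window.** Response means the threshold is met at, for example, at least 2 of the Week 16, 20 and 24 visits. The 2-of-3 cut-off is a suggestion for the sponsor to settle, since the documents give no basis for a particular value.

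Report both beside the primary rate for naive participants, switchers and total, and list any participant classified differently. Do not make a durability conclusion conditional on agreement, because that would add a decision rule to a descriptive study.

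Because the result depends on it, SAP 4.3 should also list the visits that count and say whether the denominator is planned or available visits. The Week 10 target in Table 6 should be reconciled with the visit schedule.

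The cost is SAP wording and two short derivations on data already collected. The supportive rates may be lower than the primary rate.

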5.1 INCLUSION CRITERIA

Participants are eligible to be included in the study only if all the following criteria apply:

Age

I 01. Male and female participants ≥ 18 years of age at the time of signing the informed consent.

Type of participant and disease characteristics

I 02. Confirmed diagnosis of primary ITP; for participants who previously received sutimlimab in study TDR16218, a response to sutimlimab must have been obtained, as defined by platelet count $\geq 30 \times 10^9/L$ on 2 visits at least 7 days apart.

I 03. For participants who have not previously received sutimlimab: persistent/chronic ITP (ITP lasting for ≥ 6 months) and all the following conditions:

- a) Platelet count $\leq 30 \times 10^9/L$ on 2 occasions at least 5 days apart during the Screening Period;
- b) Lack of an adequate platelet count response (as defined by maintenance of sustained platelet count $\geq 30 \times 10^9/L$ in the absence of bleeding) to at least 2 ITP treatments, 1 of which was a thrombopoietin receptor agonist. Other ITP treatments include: IVIg, anti-D immunoglobulin, corticosteroids, splenectomy, rituximab, cyclophosphamide, azathioprine, danazol, cyclosporin A, mycophenolate mofetil, or fostamatinib.
- c) If receiving weekly thrombopoietin receptor agonist dosing, the last dose must have been administered ≥ 7 days before the first dose of BIVV020. If receiving daily thrombopoietin receptor agonist dosing, the last dose must have been administered ≥ 24 hours before the first dose of BIVV020.
- d) If applicable, concurrent administration of ITP medications (eg, corticosteroids, IVIg, azathioprine, danazol, cyclosporin A, mycophenolate mofetil, or thrombopoietin receptor agonists) is acceptable provided the patient has been on a stable dose for at least 1 month. See [Section 6.8](#) for additional details.
- e) If previously dosed with rituximab, the last dose of rituximab must have been administered at least 12 weeks before the first dose of BIVV020.
- f) If previously dosed with cyclophosphamide, the last dose of cyclophosphamide must have been administered at least 4 weeks before the first dose of BIVV020.

I 04. Documented vaccinations against encapsulated bacterial pathogens (*Neisseria meningitidis*, including serogroup B where available, *Haemophilus influenzae*, and *Streptococcus pneumoniae*) within 5 years of enrollment, or as specified in [Section 8.2.6](#).

Contraception

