6.8 CONCOMITANT THERAPY

Any medication or vaccine (including over the counter or prescription medicines, vitamins, and/or herbal supplements, and rescue medication) that the participant is receiving at the time of enrollment or receives during the study must be recorded along with:

- Reason for use
- Dates of administration including start and end dates
- Dosage information including dose and frequency

Vaccinations such as seasonal influenza vaccines and other recommended vaccines and booster vaccinations are permitted as per local standard of care, investigator discretion, and local labels.

Concurrent administration of ITP medications (corticosteroids, IVIg, azathioprine, danazol, cyclosporine A, mycophenolate mofetil, or thrombopoietin receptor agonists) is acceptable provided the patient has been on a stable dose for at least 1 month. This applies for both new patients and patients who were previously receiving sutimlimab in Study TDR16218.

Corticosteroids, thrombopoietin receptor agonists, and IVIg are permitted, if the following requirements are met:

- A) Corticosteroids: the first dose of BIVV020 may be dosed only ≥ 4 days after a steroid pulse (single dose of >0.5 mg/kg prednisone equivalent or an increase in prednisone equivalent dose from prior levels) for acute ITP treatment
- B) Thrombopoietin receptor agonists: If receiving weekly thrombopoietin receptor agonist dosing, the last dose must have been administered ≥ 7 days before the first dose of BIVV020. If receiving daily thrombopoietin receptor agonist dosing, the last dose must have been administered ≥ 24 hours before the first dose of BIVV020. Thrombopoietin receptor agonists may be restarted by the Investigator if a participant has an insufficient response to BIVV020.
- C) Intravenous Ig (IVIg): the first dose of BIVV020 must be dosed ≥ 1 day after a dose of IVIg. A single dose of IVIg is allowed during the study; additional doses after the first dose must be approved by the Sponsor.

The Medical Monitor should be contacted if there are any questions regarding concomitant or prior therapy.

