6.8.1 Rescue medicine

Rescue medicines given for acute episodes of thrombocytopenia/bleeding, such as steroid pulse/bolus, thrombopoietin receptor agonists, or platelet transfusion are allowed (see above for guidance on IVIg). Additionally, increasing the dose of concomitant ITP medications to prevent or treat bleeding due to low platelet counts is allowed and would be considered rescue therapy.

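### SAP 4.3 fails a primary responder for any concomitant ITP therapy in Weeks 3 to 24, whereas the protocol and SAP Table 1 exclude only rescue therapy, and no change is declared

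*SAP*

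**What the plan says.** The primary endpoint combines a platelet criterion, met at half or more of the scheduled visits, with a condition on other ITP treatment. Protocol Table 2 and SAP Table 1 word that condition identically for naïve participants and for those coming from sutimlimab (switchers): "without receiving rescue ITP therapy, as assessed from Week 3 to Week 24". SAP 4.3, which sets out how the endpoint is derived, gives it as "No concomitant ITP therapy from Week 3 to Week 24". It then lists the drug classes that count as ITP therapy and refers to SAP 5.3 for the meaning of concomitant, which is any intervention received alongside BIVV020 in the on-treatment period.

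The protocol permits background treatment. Under criterion I 03 d in section 5.1, "concurrent administration of ITP medications (eg, corticosteroids, IVIg, azathioprine, danazol, cyclosporin A, mycophenolate mofetil, or thrombopoietin receptor agonists) is acceptable" if the dose has been stable for at least 1 month. Section 6.8 repeats this and adds: "This applies for both new patients and patients who were previously receiving sutimlimab in Study TDR16218". Section 6.8.1 describes rescue as treatment for acute episodes and says that increasing the dose of a concomitant ITP drug "to prevent or treat bleeding due to low platelet counts is allowed and would be considered rescue therapy".

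The secondary response rate has a different condition in protocol Table 2: "the lack of combination ITP therapy during this period". SAP Appendix 2, the place for changes to protocol-planned analyses, is marked as not applicable. The SAP version history reports no major changes.

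**The concern.** The SAP holds two versions of the primary endpoint. The version in the derivation section is not the protocol's. The difference falls on participants who comply with the protocol: those who entered on a permitted background drug, kept the dose unchanged and had a durable platelet response. They are successes under the protocol and SAP Table 1, and failures under SAP 4.3 as written.

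For switchers this also works against the endpoint's purpose. Protocol 3.1 says the aim is to show that a response obtained on sutimlimab is kept on BIVV020. A switcher who keeps the response on the same background drug would be recorded as not having kept it.

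The study tests no hypothesis, so the response proportion and its confidence interval are the efficacy result. The study is also open-label, and two live definitions leave room to choose between them once data have been seen.

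**Working it through.** **1. The therapy condition in each place**

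| Place | Endpoint | Therapy that disqualifies |
|---|---|---|
| Protocol Table 2 (and synopsis) | Primary | Rescue |
| SAP Table 1 | Primary | Rescue |
| SAP 4.3, criterion 2 | Primary | Any concomitant |
| Protocol Table 2 | Secondary response rate | Combination |
| SAP 4.4, criterion 3 | Secondary response rate | Any concomitant, while counts stay above the threshold |
| SAP 4.4 | Rescue endpoint | Rescue |

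The protocol keeps rescue (primary) apart from combination therapy (secondary). SAP 4.3 gives the primary endpoint the kind of condition that belongs to the secondary one.

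**2. Can concomitant be read as rescue?** No, for two reasons.
- SAP 5.3 lets an ongoing prior drug also count as concomitant, and it plans separate summaries of rescue and non-rescue concomitant ITP therapy.
- SAP 4.4 uses the word rescue where rescue is meant.

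**3. Does the disqualifying list include permitted drugs?** Protocol I 03 d names seven examples: corticosteroids, IVIg, azathioprine, danazol, cyclosporin A, mycophenolate mofetil and thrombopoietin receptor agonists. All seven are on the SAP 4.3 list.

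**4. A worked case.** Take a participant on unchanged azathioprine throughout Weeks 3 to 24, with no dose increase and no acute treatment, who meets the platelet criterion.
- Protocol and SAP Table 1 primary endpoint: responder.
- SAP 4.3 primary endpoint: non-responder.
- SAP 4.4 rescue endpoint over the same weeks: success.

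**5. Size.** The plan states no target rate or power, so there is no figure of its own to reproduce. The inputs it gives are about 12 participants, at most 6 of them switchers, and an exact Clopper-Pearson 95% interval.

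Shift per reclassified responder: 1/12 = 8.3 points in total; 1/6 = 16.7 points in a cohort of 6.

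For x responders out of n, the lower limit is the 0.025 quantile of Beta(x, n − x + 1) and the upper limit is the 0.975 quantile of Beta(x + 1, n − x). Let R be the number of platelet responders without rescue, and b the number of those on unchanged background therapy. The protocol rule gives R/n whatever b is; SAP 4.3 gives (R − b)/n. Both R and b are assumptions.

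| n, R | b = 0 (also the protocol rule) | b = 1 | b = 2 | b = 3 |
|---|---|---|---|---|
| 12, 4 | 33.3% (9.9–65.1) | 25.0% (5.5–57.2) | 16.7% (2.1–48.4) | 8.3% (0.2–38.5) |
| 12, 6 | 50.0% (21.1–78.9) | 41.7% (15.2–72.3) | 33.3% (9.9–65.1) | 25.0% (5.5–57.2) |
| 12, 8 | 66.7% (34.9–90.1) | 58.3% (27.7–84.8) | 50.0% (21.1–78.9) | 41.7% (15.2–72.3) |
| 6, 4 | 66.7% (22.3–95.7) | 50.0% (11.8–88.2) | 33.3% (4.3–77.7) | not shown |

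**6. Two side points, on which the finding does not depend.**
- Protocol 6.8.1 allows rescue "such as steroid pulse/bolus, thrombopoietin receptor agonists, or platelet transfusion are allowed". The SAP 4.3 list does not name platelet transfusion. The list is not stated to be complete, so the programming specifications could add it, but nothing in the SAP requires that.
- Thrombopoietin receptor agonists appear in the protocol as acceptable stable therapy and as rescue. Section 6.8 also says: "Thrombopoietin receptor agonists may be restarted by the Investigator if a participant has an insufficient response to BIVV020". Whether such a restart is rescue is not stated. IVIg has a similar gap between 6.8 and 6.8.1.

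**The case against.** The best reply is that this is a drafting slip. SAP Table 1 keeps the protocol wording, Appendix 2 and the version history report no change, and the programming specifications, which are not public, may apply the rescue condition. That is possible, and it is why the consequence is stated for SAP 4.3 followed as written. It does not remove the problem. SAP 4.3 leaves to the specifications which drugs count as ITP therapies, not whether their use was rescue. A specification written faithfully from 4.3 would carry the error forward.

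A second reply is that the stricter rule is conservative. Reclassifying background users can indeed only lower the rate. An undeclared change to the primary endpoint is not made acceptable by its direction, though, and if transfusion were left off the coded list the effect would run the other way.

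A third is that the study is small and descriptive, with a planned listing of all ITP therapies that flags rescue, so a reader could rebuild the protocol rate. That is true and limits the harm. The reported rate and interval would still answer a different question from the one in the protocol.

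It is also fair to say that the illustrated intervals overlap heavily, and that only the shifts of 1/12 and 1/6 follow from the planned numbers.

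**Conclusion.** The concern holds. The SAP contradicts the protocol and its own Table 1 on the therapy condition of the primary endpoint, and declares no change. Followed as written, SAP 4.3 would count compliant platelet responders on unchanged background ITP therapy as failures. Each one costs 8.3 points in the total rate with 12 participants, or 16.7 points in a cohort of 6. The total effect depends on how many responders remain on such therapy in Weeks 3 to 24, which the documents do not give; with none, the two rules agree for this group. Because the mismatch is in the primary endpoint, it must be fixed before the endpoint is derived.

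**What to change.** Before the interim analysis:

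- Restate SAP 4.3 criterion 2 as no rescue ITP therapy, as described in protocol 6.8.1, from Week 3 to Week 24. Use the rescue flag planned in SAP 5.3 and write down how it is derived.
- State that unchanged permitted background therapy does not disqualify. For dose increases, keep the protocol's own condition on purpose.
- State how a newly started ITP drug that is not given for an acute episode is scored, since a rescue-only rule may miss it. State also whether rescue counts if it is given before Week 24 but after the on-treatment period has ended.
- Name platelet transfusion in the coded list. The sponsor should reconcile protocol 6.8 and 6.8.1 on IVIg and thrombopoietin receptor agonists before coding.
- Report the rate under the no-concomitant-therapy rule as a labelled sensitivity analysis. This is useful but secondary to having one aligned definition.

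If the sponsor wants the stricter rule as primary, it should be declared and justified in Appendix 2 and SAP Table 1 changed to match. No change to time to response in SAP 4.4 is needed.

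The cost is SAP wording and a programming-specification change, plus case review of dose increases. No new data are required: protocol 6.8 already records the reason, dates and dose of each medication.
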